Rheumatology consultation and testing ²³																
Hematology consultation, testing, and biopsy ²⁴																
Clinical Labs																
Urinalysis	X											X				
CBC with differential	X		X		X		X		X		X			X		
TSH ⁹	X		X		X		X		X		X			X		
Complete serum chemistry	X		X		X		X		X		X			X		
Amylase and lipase ⁹	X											X				
Coagulation tests	X															
Vitamin B12, folate, iron, erythropoietin, haptoglobin, and transferrin levels and reticulocyte count ²⁵																
NHL Only Procedures																
PET-CT or CT scan ¹²												X (±7 days; odd cycles only)				

	Cycle 2								Cycle 3 and Beyond							
	Week 1		Week 2		Week 3		Week 4		Week 1		Week 2		Week 3		Week 4	
	D1	D4 ±1 day	D8	D11 ±1 day	D15	D18 ±1 day	D22	D25 ±1 day	D1	D4 ±1 day	D11 ±1 day	D15	D18 ±1 day	D22	D25 ±1 day	
Visit Type	Clinic Visit	Phone Call	Clinic Visit	Phone Call	Clinic Visit	Phone Call	Clinic Visit	Phone Call	Clinic Visit	Phone Call	Phone Call	Clinic Visit	Phone Call	Phone Call	Phone Call	
Lymph node core biopsy ²									X (±7 days; C6 only)							
EORTC QLQ-C30 and FACT-Lym questionnaires ¹⁴	X								X							
Advanced Solid Malignancy Only Procedures																
CT or MRI or PET-CT ¹⁵									X (±7 days; odd cycles only)							
Tumor biopsy ²									X (±7 days; C6 only)							
EORTC QLQ-C30 ¹⁴	X								X							
Study treatment dosing in-clinic ²⁰	X		X		X		X		X				X			
PK/CCI																
Blood draws for PK analysis ¹⁶					X				X (Odd cycles only)							
CCI																
Adverse events	Continuous															
Concomitant medications	Continuous															
Telephone contact ¹⁸		X		X		X		X		X	X		X	X	X	X

Table 3: Schedule of Assessments: End-of-Treatment and Beyond (Parts A and B)

Activity/Assessment	End-of-Treatment (EoT) Visit	Safety Follow-up Call ²²	Durability of Response and Survival Follow-up ¹⁹
	≤ 14 Days Post Last Dose	30 Days Post-Last Dose	Every 3 months for 1 year after the safety follow-up call
		+ 7 days	± 7 days
Clinical Assessments			
Patient weight	X		
Vital Signs (BP, pulse, temp) ⁴	X		
Complete physical exam	X		
12-lead ECG ⁵	X		
Echocardiogram or MUGA ⁶	X		
Ophthalmic exam ⁷	X		
ECOG	X		
Rheumatology consultation and testing ²³	As clinically indicated		
Hematology consultation, testing, and biopsy ²⁴	As clinically indicated		
Clinical Labs			
Urinalysis	X		
CBC with differential	X		
TSH ⁸	X		
Complete serum chemistry	X		
Amylase and lipase ⁹	X		
Coagulation tests	X		
Serum hCG pregnancy test ¹⁰	X		

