2.2.2. Efficacy Endpoints

Disease response will be evaluated according to RECIST 1.1 (advanced solid malignancies and melanoma ([Appendix 4](#))) or Lugano Classification (NHL) ([Appendix 3](#)) and will include the following:

- **Overall response rate (ORR):** = proportion of patients who have a response of partial response (PR) or complete response (CR).
- **Duration of response (DOR):** the duration of time from first meeting CR or PR measurement criteria (whichever occurs first) until the first date that PD recurrence is objectively.
- **Disease control rate (DCR):** DCR = proportion of patients who have a response of CR, PR, and Stable Disease (SD) ≥ 16 weeks.
- **Duration of disease control:** the duration of time from date of first study treatment until the first date that PD is objectively documented.
- **Progression-free survival (PFS):** the duration of time from date of first study treatment until the first date that PD is objectively documented or death due to any cause.
- **Overall survival (OS):** the duration of time from date of first study treatment until death from any cause .

- **Time to Progression (TTP):** The duration of time from date of first study treatment until the first date that PD is objectively documented or death due to PD.

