In Part C, a cohort of patients with melanoma that have progressed on an anti-PD1 or anti-PD-L1 antibody will be treated with KPT-9274 (at a dose that cleared DLT evaluation in Part A) + nivolumab. Two dose levels of KPT-9274 (30 and 40 mg) in combination with nivolumab will be tested in parallel. Patients will be enrolled first into the 30 mg cohort. Patients will be treated with 30 or 40 mg KPT-9274 three times a week every other day (Days 1, 3, 5, 8, 10, 12, 15, 17, 19, 22, 24, and 26) during each 28-day cycle in combination with a standard dose and schedule of nivolumab (480 mg on Day 1 of each 28-day cycle). A maximum of 10 patients may be enrolled at each dose level. Treatment will continue until disease progression, unacceptable AEs or toxicity that cannot be managed by supportive care, patient's withdrawal of consent, Investigator decision to discontinue study treatment, pregnancy, death, or Sponsor decision to terminate the study. A safety review committee will evaluate all available data from both cohorts after the last patient enrolled has been observed for at least 2 cycles to determine the RP2D.

Additional dose levels (20 mg or 60 mg) might be evaluated if an optimal dose is not identified and the safety review committee is in agreement. The definition of a DLT is the same as described in Parts A and B. Response will be assessed every 8 weeks per RECIST 1.1 criteria ([Appendix 4](#)).

All phases of the study will be comprised of Screening, Treatment, and Follow-up periods.

Screening will be performed within 30 or 14 days prior to the start of therapy (i.e., Day -30 to Day -1, Day -30 to Day -14, or Day -14 to Day -1), as summarized in [Table 1](#) and [Table 5](#). During the Treatment period, procedures are to be performed during clinic visits prior to the administration of study treatment on those days as presented in [Table 1](#), [Table 2](#), [Table 5](#) and [Table 6](#). The Follow-up period includes the EOT visit, the Safety Follow-up visit, and Durability of Response and Survival Follow-up; see [Table 3](#) and [Table 7](#) for assessments to be completed during the Follow-up period.

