3.3. Treatment Duration

Treatment cycles are 28 days long. A patient may continue to receive KPT-9274 until that patient experiences PD, withdraws consent, is lost to follow-up, experiences intolerable toxicity which precludes further treatment with KPT-9274, or treatment is discontinued at the discretion of the Investigator or the Karyopharm Medical Monitor.

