7.3.3.1. CT, MRI, PET-CT, or Imaging Methodology Per Investigator Discretion

Disease response is based on tumor measurement using computed tomography (CT) scans or, magnetic resonance imaging (MRI) scans, or PET-CT, or imaging methodology per Investigator discretion. Scans will be performed at Screening (Day -30 to Day -1), then every 8 weeks \pm 7 days (e.g., Day 1 of odd numbered cycles) until disease progression or the EoT visit. EoT scan is only required for patients who end treatment for reasons other than disease progression.

The same scan modality should be used for all assessments.

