9.5. Efficacy Analysis

Disease response will be evaluated according to RECIST 1.1 (advanced solid malignancies) [Appendix 4](#)) or Lugano Classification (NHL) ([Appendix 3](#)) and will include the following endpoints: Time-to-event efficacy endpoints will be performed using the same Kaplan-Meier method for estimation of summary statistics, and will include the 25th, 50th (median) and 75th percentiles, associated two-sided 95% Cis (if estimable), and number of events and censored observations.

- Overall response rate (ORR): The analysis of ORR will be performed by calculating the point estimate of the percentage of patients who have either CR or PR, presented as the number and percentage of patients, including a two-sided 95% CI.
- Duration of response (DOR): the duration of time from first meeting CR or PR measurement criteria (whichever occurs first) until the first date that Progressive Disease (PD) recurrence is objectively documented. Patients without documented PD will be censored on the date of last disease assessment.
- Disease control rate (DCR): The analysis of DCR will be similar to that described for ORR, for patients who achieve CR, PR, or SD for ≥ 16 weeks.
- Duration of disease control: the duration of time from date of first study treatment until the first date the PD is objectively documented. Patients without documented disease progression will be censored on the date of last disease assessment.
- Progression-free survival (PFS): the duration of time from date of first dose of study treatment until the first date that PD is objectively documented or death due to any cause. Patients without documented PD will be censored on the date of last disease assessment.
- Overall survival (OS): the duration of time from date of first dose of study treatment until death from any cause. Patients who withdraw from the study or are alive at the time of data analysis will be censored on the date of last contact.

- TTP: The duration of time from date of first dose of study treatment to date of PD. Patients who withdraw from the study or are alive at the time of data analysis per Section 2.2.2 without documented DD will be censored on the date of last contact.

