APPENDIX 4. RECIST VERSION 1.1

(Modified from [Eisenhauer 2009](#))

All patients will have their BEST RESPONSE on study classified as outlined below:

Complete Response (CR)

Disappearance of all target lesions. Any pathological lymph nodes (whether target or non target) must have reduction in the short axis to <10mm.

Partial Response (PR)

At least a 30% decrease in the sum of diameters of target lesions, taking as reference the baseline sum diameters.

Stable Disease (SD)

Steady state of disease. Neither sufficient shrinkage to qualify for PR nor sufficient increase to qualify for PD.

Progressive Disease (PD)

At least a 20% increase in the sum of diameters of measured lesions taking as references the smallest sum of diameters recorded since the treatment started. In addition to the relative increase of 20%, the sum must also demonstrate an absolute increase of at least 5 mm.
Appearance of one or more new lesions will also constitute progressive disease.

Response Duration

Response duration will be measured from the time measurement criteria for CR/PR (whichever is first recorded) are first met until the first date that recurrent or progressive disease is objectively documented, taking as reference the smallest measurements recorded since the treatment started.

Stable Disease Duration

Stable disease duration will be measured from the time of start of therapy until the criteria for progression are met, taking as reference the smallest measurements recorded since the treatment started.

Evaluation of Best Overall Response – Patient with Target (= non-target) disease

Target lesions	Non-Target lesions	New Lesions	Overall response
CR	CR	No	CR
CR	Non-CR-Non-PD	No	PR
CR	NE	No	PR
PR	Non-PD/or not all evaluated	No	PR
SD	Non-PD/or not all evaluated	No	SD

Target lesions	Non-Target lesions	New Lesions	Overall response
Not all evaluated	Non-PD	No	NE
PD	Any	Yes or No	PD
Any	PD	Yes or No	PD
Any	Any	Yes	PD

Evaluation of Best Overall Response – Patient with Non-Target Disease

Non-Target lesions	New Lesions	Overall response
CR	No	CR
Non-CR-Non-PD	No	Non-CR/Non-PD ¹
Not all evaluated	No	NE
Unequivocal PD	Yes or No	PD
Any	Yes	PD

Note: Patients with a global deterioration of health status requiring discontinuation of treatment without objective evidence of disease progression at that time should be reported as “*symptomatic deterioration*”. Every effort should be made to document the objective progression even after discontinuation of treatment.

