# 4.1. EFFICACY ENDPOINTS

Please refer to Table 4-1 below for primary and secondary endpoints and the corresponding definitions

Table 4-1 Efficacy Endpoints and Definitions

Endpoint	Definition	
Secondary Endpoints		
Objective response rate (ORR)	Proportion of patients who have a response of partial response (PR) or complete response (CR)	
Duration of response (DOR)	The duration of time from first meeting CR or PR measurement criteria (whichever occurs first) until the first date that PD recurrence is objectively documented or death due to any cause	
	Please refer to Table 4-3 for details on the outcome and censoring definitions.	
Progression-free survival (PFS)	The duration of time from date of first study treatment until the first date that PD is objectively documented or death due to any cause.	
	Please refer to Table 4-2 for details on PFS outcome status (PFS event vs. censored) and censoring definitions.	
Overall survival (OS)	Duration from the date of first study treatment until death due to any cause. If death event did not occur during the follow-up period, the patient is censored at the date of discontinuation from the study (i.e. withdrawal of consent), or date of last participating visit (e.g., a telephone contact with patient status being alive) on or before database cutoff date, whichever occurs first.	
Time to Progression (TTP)	The duration of time from date of first study treatment until the first date that PD is objectively documented or death due to PD	

Disease control rate (DCR)	Proportion of patients who have a response of CR, PR, and Stable Disease (SD) ≥ 16 weeks.
Duration of disease control	Duration of disease control is defined among patients achieving disease control as the duration from the date of first meeting the response measurement criteria for disease control to the date of PD or death due to disease progression.  Please refer to Table 4-3 for details on the outcome and censoring definitions.

Table 4-2 PFS and DOR outcome and censoring definition

Situation	Date of event or censoring	Outcome
No baseline disease assessment	Date of first study treatment	Censored
No adequate post-baseline disease status assessment unless death occurs prior to first post-baseline assessment	Date of first study treatment	Censored
Death before PD without a gap of 2 or more consecutively missed scheduled disease status assessment before death	Date of death	Event

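### For RECIST-assessed patients, progression found at an on-time week-16 scan literally satisfies the stable-disease part of DCR, and whether it counts depends on the scan day within the ±7-day window

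*Protocol*

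**What the plan says.** **Endpoint.** Protocol 2.2.2 defines DCR as the "proportion of patients who have a response of CR, PR, and Stable Disease (SD) ≥ 16 weeks". SAP Table 4-1 uses the same words. Protocol 9.5 analyses it like ORR, "for patients who achieve CR, PR, or SD for ≥ 16 weeks".

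**Clock.** The only rule on how long stable disease has lasted is in the RECIST appendix (Protocol Appendix 4): "Stable disease duration will be measured from the time of start of therapy until the criteria for progression are met". The clock stops on the date of progression, not on the last scan that showed stable disease. Appendix 3 (Lugano, for NHL) defines stable disease but gives no rule for its duration.

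**Schedule.** For Part C, Protocol 3.1 says: "Response will be assessed every 8 weeks per RECIST 1.1 criteria". For solid tumours, Protocol 7.3.3.1 sets scans every 8 weeks ±7 days, "e.g., Day 1 of odd numbered cycles) until disease progression or the EoT visit". The Cycle 3 and Beyond columns of Protocol Table 2 carry the entry "X (±7 days; odd cycles only". Protocol 3.3 adds: "Treatment cycles are 28 days long". SAP 2.5 sets Day 1 as the date of first study treatment.

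**What is absent.** Neither document says which scan must show stable disease, whether PD at the week-16 scan fails the criterion, or how the ±7-day window is handled for DCR. SAP Tables 4-2 and 4-3 give event and censoring rules for PFS, DOR, TTP and duration of disease control only. SAP 1.7 states that the protocol's statistical section was not modified.

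**The concern.** A 16-week disease control rate should describe patients whose disease had not progressed at about 16 weeks. Here the threshold is an at-least threshold, the clock ends on the progression date, and the second scan lands on the threshold itself. A scan that documents progression can therefore supply the last day needed to qualify. At nominal timing, the stable-disease part of DCR shows only that no progression was found at week 8.

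The result also depends on booking. Among patients with the same findings at both scans, one scanned late in the permitted window qualifies and one scanned early does not.

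The Protocol Synopsis lists DCR among the primary endpoints of the Dose Expansion, if conducted, and among the secondary endpoints of Parts A, B and C. SAP Table 4-1 lists it as secondary. Two programmers working from the same data could report different values, one applying the Appendix 4 clock and the other requiring stable disease at week 16.

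**Working it through.** **1. Reproduce the plan's visit days.** Target day of Day 1 of cycle c = 1 + 28 × (c − 1).
- C3D1: 1 + 28 × 2 = Day 57, as in SAP Table 2-1-1.
- C4D1: 1 + 28 × 3 = Day 85, as in the same table.
- C5D1: 1 + 28 × 4 = Day 113.

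The SAP table covers laboratory visits. It is used here only to confirm the day count.

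**2. Stable-disease duration at the second scan.** Scans on odd cycles put the first at C3D1 (56 days, week 8) and the second at C5D1. Progression date minus first-dose date = 113 − 1 = 112 days = 16.0 weeks, which meets the threshold with no margin.

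**3. The window.** ±7 days gives Days 106 to 120, which is 15 permitted days, or 105/7 = 15.0 to 119/7 = 17.0 weeks after first dose.
- PD on Days 113-120 gives 112 days or more: 8 of 15 days qualify.
- PD on Days 106-112 gives 105-111 days: 7 of 15 do not.
- If duration is counted with +1 day, Day 112 also qualifies and the split is 9 to 6. The documents do not say which convention applies to stable-disease duration.

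**4. A precondition.** The patient must have had stable disease at the first scan. If PD is the only post-baseline result, there is no stable disease to time.

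**5. Illustrative size.** The documents give no progression rate. Assume exponential time to progression with median m days, S(t) = 0.5^(t/m), and scans on nominal days. Under the Appendix 4 clock the share counted is S(56), no PD at week 8. The share progression-free at week 16 is S(112). With scan days spread evenly over the window, the share counted is roughly S(112) + 8/15 × [S(56) − S(112)].

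| Median m (assumed) | Counted, nominal days: S(56) | Progression-free at week 16: S(112) | Difference | Counted, evenly spread scans |
|---|---|---|---|---|
| 45 days | 0.422 | 0.178 | 0.244 | 0.308 |
| 61 days | 0.529 | 0.280 | 0.249 | 0.413 |
| 91 days | 0.653 | 0.426 | 0.227 | 0.547 |

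The difference on nominal days is about 23 to 25 percentage points across this range. It overstates the effect for the reasons given under the objection.

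**The case against.** The strongest reply is that the plan is unclear rather than wrong. No DCR definition points to the Appendix 4 paragraph, and stable disease of at least 16 weeks can be read as stable disease documented at 16 weeks. SAP Table 4-1 gives this reading some support. It starts duration of disease control when the criteria for disease control are first met. If the 16 weeks is part of those criteria, a Day-113 progressor attains control on the progression date, with zero duration. This does not settle the matter, because a week-8 start is also possible, no passage states the documented-at-week-16 reading, and the one written clock gives the opposite answer.

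Four stronger readings are tempting, and the documents do not support them.
- *That the flaw is shown for all patients.* The clock is in the RECIST appendix only. For NHL the rule is missing, so nothing is demonstrated either way.
- *That a patient still stable on Days 106-112 who stops without progression falls short of 16 weeks.* Appendix 4 ends the clock only at progression, and no censoring rule is given for DCR. The Protocol also requires an end-of-treatment scan for patients who stop for reasons other than progression, and provides for follow-up scans where feasible and clinically indicated. The outcome for such a patient is unstated.
- *That everyone who progresses between weeks 8 and 16 is miscounted, so that 53% against 28% (median 61 days) is the bias.* A patient with PR at week 8 and PD at week 16 counts under either rule. An end-of-treatment scan before Day 113 can date progression earlier. Dropout and deaths are ignored, and the progression rate is assumed.
- *That a week-16 progressor would open full expansion.* The futility rule has its own approximate wording, about 16 weeks in Protocol 9.5.1 and about 8 weeks in 6.2.7, and is not tied to the DCR definition. Those two sections must be reconciled separately.

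It is also fair to say that DCR is descriptive, with an exact 95% confidence interval and no hypothesis test, and that PFS from the same scans would show the early progression.

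**Conclusion.** The point holds for patients assessed by RECIST 1.1, meaning solid tumours and melanoma. The written clock applied to the written schedule lets stable disease at week 8 followed by PD at a second scan on Days 113-120 count in DCR, and excludes the same finding on Days 106-112. For NHL the rule is undefined. This part rests only on the documents' day counts and on taking duration as the difference in dates. The +1 convention moves the boundary by one day and does not remove it.

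The size is less certain. Under assumed exponential progression with median 45-91 days and nominal scan days, the share counted is at most about 42%-65%, against 18%-43% progression-free at week 16. The gap should be read as an upper bound.

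Severity is moderate. No error rate or power is affected, and DCR is one of seven efficacy endpoints named for an optional expansion. Still, its label would claim more than the data show, and the reported value would depend partly on scan booking.

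**What to change.** In SAP Table 4-1 and Protocol 2.2.2 and 9.5, define the stable-disease part of DCR, for both RECIST and Lugano, as stable disease without PD documented on a scan at the nominal week-16 assessment (C5D1) or later. State also that:
- a scan within the permitted −7-day window (Day 106 or later) satisfies the 16-week criterion. This has to be written out, because Day 106 is 105 days, or 15.0 weeks, and would otherwise conflict with the literal threshold;
- PD at that scan is not disease control;
- the Appendix 4 stable-disease duration is not used to qualify a patient for DCR;
- a patient with no evaluable scan at or after that point, and no CR or PR, counts as not controlled.

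The cost is a few sentences in each document and no new scans. The reported DCR becomes less favourable, partly because patients with a missed or non-evaluable C5D1 scan and nothing later will count as not controlled.

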12 NHL disease assessment is preferably based on PET/CT for FDG-avid lymphomas, or CT for non-FDG-avid lymphomas. PET/MRI or MRI may be substituted if CT is contraindicated. Scans are performed at Screening and after every 8 weeks \pm 7 days (e.g., Day 1 of odd numbered cycles) until disease progression or the EoT visit and Durability of Response and Survival Follow-up. EoT scan is only required for patients who end treatment for reasons other than disease progression. The same scan modality should be used for all assessments. Durability of Response and Survival Follow-up scan is only for patients who have not progressed.

13 Bone marrow biopsies and/or aspirates will be taken within 30 days prior to first dose (baseline) to assess NHL involvement in bone marrow. The bone marrow biopsy will be repeated whenever clinically indicated, at the discretion of the Investigator, to confirm CR/PR in only those patients who had NHL with known bone marrow involvement prior to dosing (see Section 7.3.2.2).

14 Patient will complete QoL questionnaires before they have any study procedures (including discussions with medical personnel and administration of study treatment) at these visits (see Section 7.3.1.1).

15 Advanced solid malignancies: CT, MRI, or PET-CT scans will be performed at screening (Day -30 to Day -1), then every 8 weeks \pm 7 days (e.g., Day 1 of odd numbered cycles), until disease progression or the EoT visit and Durability of Response and Survival Follow-up. EoT scan is only required for patients who end treatment for reasons other than disease progression. The same scan modality should be used for all assessments. Durability of Response and Survival Follow-up scan is only for patients who have not progressed.

16 See Section 7.4 for timing of blood samples to be collected for PK analysis. Please note that if a patient's dose is changed, blood sampling for PK (as requested for C1D1) should be repeated on the first day of dose change at the same times as described for C1D1, C1D2, and C1D3. If the dose is missed, PK blood draws will not be collected on that day.

CCI

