5.2. Discontinuation of Study Treatment and/or Withdrawal of Patients from the Study

The Investigator may remove a patient from study treatment after consultation with the Karyopharm Medical Monitor for any of the following reasons:

- Unacceptable AEs or toxicity that cannot be managed by supportive care
- Any medically appropriate reason (e.g., clinical progression) or significant protocol violation, in the opinion of the Investigator

The Investigator must remove a patient from study treatment for any of the following reasons:

- Disease progression per response criteria
- Patient withdraws consent to continue study treatment
- Pregnancy

Patients who are removed from study treatment by the Investigator are not permitted to restart study treatment.

Patients may discontinue study treatment for any reason. Patients who choose to discontinue study treatment should be encouraged to continue in the study so that follow-up information on disease progression and survival status may be obtained. Patients may elect to withdraw consent and decline further participation in the study at any time. If a patient withdraws consent after completing Cycle 1, he/she may request to re-enter the study, if it occurs within 28 days since the last dose, by re-signing consent. This is permitted based on the Investigator's discretion and after consultation with the Karyopharm Medical Monitor.

The reason for the patient's discontinuation of study treatment/withdrawal from the study must be recorded on the eCRF.

All patients will be followed until PD, withdrawal of consent, occurrence of any withdrawal criteria, intolerable toxicity precluding further treatment with study treatment, death or loss to follow up.

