 - **Rationale:** Address request from FDA in Study May Proceed Letter dated 03 March 2016 to include sampling to capture large cardiac safety signals. The time matched C1D26 pre- and post-dose PK samples and ECGs will allow pre- and post-dose (at estimated KPT-9274 T_{max}) assessment of cardiac changes after 4 weeks of dosing. These data will allow comparison of cardiac changes after one dose (C1D1) and after 4 weeks of dosing (C1D26).
 - **Modified Sections:** Schedule of Assessments (Table 1 and footnote #5), Section 6.2.2.5.

- Changed frequency of disease assessment scans for solid malignancy patients from every 6 weeks to every 8 weeks; indicated that EoT scans are only required for patients who end treatment for reasons other than disease progression.
 - **Rationale:** Standardize frequency of disease assessments for solid malignancy and NHL patients; eliminate EoT scan for patients who had a disease assessment scan at the time of their disease progression prior to EoT visit.
 - **Modified Sections:** Schedule of Assessments (Tables 1-3), Sections 6.2, 9.3.2, 9.3.3.

CCI

References

- Removed two references that do not appear in the protocol.
 - **Rationale:** Correction of text errors.
 - **Modified Section:** Section 13.

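### Patients stopped for clinical progression have no named row in the SAP censoring tables and may miss the end-of-treatment scan, so PFS and TTP may be overstated

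*Protocol*

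**What the plan says.** Protocol 5.2 gives two separate routes off treatment for a failing patient. The investigator must remove a patient for "Disease progression per response criteria", and may remove a patient for "Any medically appropriate reason (e.g., clinical progression) or significant protocol violation, in the opinion of the Investigator". The note in Appendix 4 covers "Patients with a global deterioration of health status requiring discontinuation of treatment without objective evidence of disease progression at that time". Such patients are recorded as symptomatic deterioration, and the note adds: "Every effort should be made to document the objective progression even after discontinuation of treatment".

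On imaging, 7.3.2.1, 7.3.3.1, footnotes 12 and 15 to Tables 1-3 and footnote 20 to Tables 5-7 all say: "EoT scan is only required for patients who end treatment for reasons other than disease progression". Scans on treatment are 8-weekly. Scans after treatment are 3-monthly for a year in patients who have not progressed, and only where feasible and clinically indicated.

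SAP Tables 4-2 (PFS, DOR) and 4-3 (TTP, duration of disease control) have no row for clinical progression or symptomatic deterioration. The rows that reach these patients are:

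- "No adequate post-baseline disease status assessment unless death occurs prior to first post-baseline assessment": censored at first dose. Table 4-3 has the same row, limited to death due to progression.
- Death before progression with fewer than two consecutive missed assessments: an event at death. In Table 4-3 the death must be due to progression.
- No progression or death by data cut, consent withdrawal, loss to follow-up, new antineoplastic treatment or a two-assessment gap: censored at the last adequate assessment. Table 4-3 adds death from other causes.

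SAP 4.2 has no sensitivity analysis for these patients.

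**The concern.** Kaplan-Meier estimation assumes that a censored patient has the same outlook as those still at risk. A patient withdrawn because the disease is visibly getting worse does not. Censoring such a patient at the last clean scan, or at first dose, removes a failure from the numerator and the risk set together, and the curve rises.

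The population has exhausted useful standard options and is progressing at entry, and the first scheduled scan is at about week 8, so some patients may fail clinically before any post-baseline image. A scan at the end of treatment would often settle the matter, which is why the wording of the waiver matters. The synopsis lists PFS and TTP among the primary endpoints of the Dose Expansion Phase, although SAP Table 4-1 places them under secondary endpoints.

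**Working it through.** The plan states no PFS or TTP figure, so there is none to reproduce. The 8-week scan interval and the censoring rows come from the documents. Everything else below is assumed.

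**Upper limit, by hand.** Let q be the chance of failing in an 8-week interval and f the share of failures that are clinical only, unscanned and all censored at the preceding scan. Each such patient leaves the risk set at the start of the interval. Interval survival therefore changes from 1 - q to

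(1 - q) / (1 - f q),

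and 24-week PFS is its cube. With a true median of 8 weeks, q = 0.500. With 16 weeks, q = 1 - 2^(-0.5) = 0.293. At f = 0.3 and a 16-week median: 0.7071 / (1 - 0.3 × 0.293) = 0.775, and 0.775 cubed = 46.6%, against a true 35.4%.

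**With the SAP's death and new-therapy rules.** Simulation of 200,000 patients per scenario. A clinical-only failure becomes a PFS event if death follows before two missed 8-weekly assessments and before new therapy; otherwise the patient is censored at the last scan. *Low* assumes a median of 6 weeks from failure to death and no new therapy. *High* assumes 16 weeks and 30% starting new therapy.

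| True median | f | 24-week PFS if counted as events | SAP rows, low | SAP rows, high | All censored (formula) |
|---|---|---|---|---|---|
| 8 wk | 10% | 12.5% | 13.3% | 14.1% | 14.6% |
| 8 wk | 20% | 12.5% | 14.4% | 16.1% | 17.1% |
| 8 wk | 30% | 12.5% | 15.4% | 18.1% | 20.4% |
| 16 wk | 10% | 35.4% | 36.8% | 37.7% | 38.7% |
| 16 wk | 20% | 35.4% | 37.9% | 40.7% | 42.4% |
| 16 wk | 30% | 35.4% | 39.6% | 43.6% | 46.6% |

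The third column is the exact value; the simulated references lay within 0.2 points of it. The overstatement runs from about 1 point (13.3 - 12.5 = 0.8) to about 8 (43.6 - 35.4 = 8.2). Across scenarios 29% to 75% of clinical-only failures still became events through death. Those left censored were 2% to 21% of all patients, and patients censored at first dose were 1% to 11% of all patients. Where an end-of-treatment scan documented progression, the estimate came within 1 point of the reference.

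**Scale.** With 45 uncensored patients, the standard error of a 35.4% estimate is sqrt(0.354 × 0.646 / 45) = 7.1 points.

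**Ten-patient example.** Failures at weeks 3, 5, 8, 8, 8, 16, 16, 16, 24 and 32, the first two clinical only. Counting both, 16-week PFS is 2/10 = 20%. Censoring both at first dose gives 2/8 = 25%. If one of them dies at week 12 and counts, it is 2/9 = 22%.

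Two conventions matter. The simulation counts a death before week 16 as an event when there is no post-baseline scan; the SAP row does not say whether its first assessment means scheduled or performed, and the stricter reading would censor more. It also counts missed assessments on the 8-week grid; the sparser schedule after treatment would let more deaths count.

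**The case against.** The strongest reply is that the plan is not silent. PFS and TTP are defined by objectively documented progression or death, and Protocol 9.5 censors PFS without documented progression at the last disease assessment. The SAP rows give every such patient an outcome, and early deaths count. A reader might infer that these patients have no scoring rule at all, or that all of them are censored. The documents support neither: what is missing is a named row and a sensitivity analysis.

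On the scan, a reader might infer that the protocol excuses these patients. The more natural reading is the opposite. Section 5.2 lists clinical progression apart from progression per criteria, which makes it a reason other than disease progression, and Appendix 4 asks that objective evidence be sought. The amendment log, as background, gives the waiver's purpose as to "eliminate EoT scan for patients who had a disease assessment scan at the time of their disease progression prior to EoT visit". This stands. Even so, the scan rule does not say which kind of progression it means, and a site could take clinical progression as covered. Later scans are conditional, and 5.2 allows follow-up to end on any withdrawal criterion.

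The consequence is also limited. These are single-arm descriptive estimates. The MTD rests on DLTs, the RP2D on safety and tolerability, and futility on response or stable disease. ORR and DCR do not use these censoring rows.

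**Conclusion.** The point holds as a risk of upward bias in PFS and TTP. DOR and duration of disease control may be affected in the same way, among patients who had already achieved response or disease control. The direction follows from the censoring rows. The size does not: about 1 to 8 points of 24-week PFS rests on assumed failure times, an assumed 10% to 30% clinical-only share with the scan skipped, and assumed rates of death and new therapy. That ranges from negligible to roughly one standard error in a 45-patient expansion that may not take place.

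Two stronger inferences fail. A reader might expect median PFS to jump by a whole scan interval. Such jumps are artefacts of the 8-week grid: with a true median of exactly 8 weeks the curve sits at 0.500 on a scan date and even a 1% share moves the median to 16 weeks, whereas at 7 weeks a 10% share moves nothing, nor does 30% at 9, 10 or 11 weeks. A reader might also expect failures before week 8 to inflate duration of disease control. The SAP restricts that endpoint to patients who achieved disease control, so those patients are not in it.

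The change should be made, because the rows as written would yield informatively censored estimates and the reader could not see how many patients were involved.

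**What to change.** 1. Protocol footnotes 12, 15 and 20, and 7.3.2.1 and 7.3.3.1: reconcile the scan wording with 5.2 and Appendix 4, so that the waiver covers only progression already documented objectively under the response criteria.
2. SAP 4.1 and 4.2: keep the primary analysis. Add a sensitivity analysis of PFS and TTP, and of duration of disease control among those who achieved it, that counts discontinuation for clinical progression or symptomatic deterioration as an event on the discontinuation date. Report the number of such patients beside each Kaplan-Meier estimate.

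The cost is an end-of-treatment scan for a few patients whom a site might have excused, one extra table, and a less favourable sensitivity estimate. Section 5.2 already requires the reason for discontinuation on the eCRF and SAP 3.1 tabulates it, but the documents do not show the answer options. The form must separate clinical from objective progression for the analysis to be possible. No sample size or error rate changes.
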